5.8.3. Clinical Laboratory Measurements

Central laboratory measures for chemistry and hematology parameters will be explored through two methods:

First, summaries will focus on study population changes with the intent of identifying deviations on a large scale across time. This approach for continuous variables summarizes both the actual results (at both baseline and post-baseline) and the change from baseline results at each post-baseline scheduled visit. Descriptive statistics include number of subjects, mean, median,

standard deviation, minimum, Q1, Q3, and maximum values for each of the 5 blood collection schedule group (Schedule I through M) by treatment group.

Second, shift tables based on baseline categories of low/normal/high/total will be provided for each post-baseline visit by treatment group. In addition, line plots of change from baseline in lab values over time will be presented with visit plotted on the x-axis and lab values on the y-axis, with treatment group side by side at each time point. In addition to the shift analyses, number (and percentage) of subjects with lab values meeting the treatment-emergent PCSV criteria at least once during the TEAE period will be summarized. These laboratory parameters will be presented by the biological functions defined in Section 4.7.3. Subject listings of laboratory measurements that meet treatment-emergent PCSV criteria will be provided.

5.8.4. Analysis of Vital Signs

All collected vital sign measures (pulse rate, respiratory rate, sitting blood pressures, and temperature) will be explored through summaries of both the actual measurements (at both baseline and post-baseline) and the change from baseline measurements at each post-baseline scheduled visit. Descriptive statistics include number of subjects, mean, median, standard deviation, minimum, Q1, Q3, and maximum values for each treatment group. In addition, body weight will be summarized in the same fashion.

The obtainment of blood pressure in infants, without cause or suspicion of underlying abnormalities is not routinely done in the outpatient pediatric setting. Specialized equipment, not routinely present in pediatric physician offices, is required. As a result of the issues surrounding the accurate obtainment of blood pressures in the study's infant population, the study protocol was revised to allow investigators to record that blood pressures are not able to be obtained. In many instances blood pressure results are not available, and in instances where results have been obtained, the accuracy of the recordings can be questioned. As a result, no shift table or treatment-emergent PCSV analyses will be performed on blood pressure measurements.

The protocol allows for the measurement of subject temperature using different modalities, eg, temporal, axillary, rectal and tympanic. Temperatures measured using different modalities are not equivalent and conversions are necessary to allow comparison. Furthermore, as the child ages throughout their time participating in the study, elevations in temperature that would be of concern change. Therefore due to the complexities to standardize reporting of temperatures and to accommodate changes reflecting the age of the child over time, no shift table or treatment-emergent PCSV analyses will be performed on temperature measurements.

Only the number (and percentage) of subjects with pulse rate and respiratory rate values meeting the treatment-emergent PCSV criteria at least once during the TEAE period will be summarized. Subject listings of vital sign measurements that meet treatment-emergent PCSV criteria will be provided.

5.8.5. Physical Exams

The number (n) and percentage (%) of subjects with abnormal physical examination at baseline and each scheduled post-baseline assessment will be summarized for each treatment group.

5.9. Analysis of Pharmacokinetic and Antibody Data

The analyses in this section will be performed by the Bioanalytical or Pharmacometrics groups.

5.9.1. Analysis of Pharmacokinetic Data

Concentration data will be summarized by descriptive statistics at each nominal time point. Pooled individual data and mean REGN2222 concentration-time plots will be produced.

These data may be utilized in a population PK analysis. If conducted, results be reported separately.

5.9.2. Analysis of Anti-drug Antibody Variables

Listings of ADA positivity and titers will be presented by subject and time point. Prevalence of ADA including treatment-emergent and treatment-boosted ADA will be assessed as absolute occurrence (n) and percent (%) of subjects.

ADA titer levels and persistent ADA will also be evaluated.

Possible correlation between changes in drug concentration and ADA assay response will be evaluated. Additionally, possible correlation between ADA assay response and safety or efficacy will also be assessed.

5.10. Analysis of Pharmacodynamic/Genomics Variables

Pharmacogenomic analysis of subject genetic variants associated with adverse events or efficacy may also be performed. Statistical plan for subject genetic analysis will be described in a separate document.

5.11. Analysis of RSV RT-PCR Data

The number (and percentage) of subjects with at least one nose swab collected and of subjects with at least one RSV positive nose swab will be summarized respectively for the FAS by treatment group.

A listing of local laboratory RSV RT-PCR assay results that were used to incur a primary endpoint event will be provided.

5.12. Analysis of Multiplex Respiratory Pathogen RT-PCR Data

Nose swab specimens tested negative on the RSV Lyra RT-PCR assay will be tested on the multiplex RT-PCR respiratory panel for alternative etiologies of RSV-negative respiratory tract infections.

The number and percentage of **subjects** with non-RSV medically attended respiratory illness (as defined in Section 5.7.5.3) who tested positive for any and each type of non-RSV pathogen on the RT-PCR multiplex respiratory panel will be summarized by treatment group. The denominator used to calculate percentage will be the number of FAS subjects in each treatment group.

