### 6.3.3.3. Virology Testing

Nose swabs collected from respiratory unscheduled visits (Section 6.2.3) will be tested at a central laboratory for RSV by RT-PCR. Positive samples will be sequenced for viral subtyping and resistance monitoring. Further details will be provided in the study manual.

In addition, nose swab specimens negative for RSV using the RT-PCR assay utilized for determination of primary endpoint cases will be evaluated using a second and distinctly different RT-PCR multiplex respiratory panel. The multiplex assay will be performed to determine the presence of other common respiratory pathogens in nose swabs. This multiplex evaluation will only be conducted on RSV negative swabs collected from subjects and will not be used in the primary analyses of the primary and secondary efficacy endpoints.

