# 8.4. Exploratory Endpoints

The exploratory endpoints are the following: Total number of RSV-associated medical visits (hospital, ER, UC, or pediatric visitsa) for each subject and associated treatments or procedures at these visits

- Total number of medical visits (hospital, ER, UC, or pediatric visitsa) for each subject and associated treatments or procedures at these visits, during the study period excluding the initial RSV-associated medical visits.
- Number of RSV-confirmed hospitalizations (defined as stay in hospital [or its ER] for 24 hours or longer)
  - Number of days with RSV-associated mechanical ventilation
  - Number of days with RSV-associated supplemental oxygen
- Length of stay in hospital for RSV-associated illness

<sup>a A pediatric clinic visit represents any outpatient medically attended visit that could include, but is not limited to, a pediatric clinic visit, a primary physician office visit, a family physician visit, or a study site visit.

- Number of missed days of work for parent(s) or guardian(s) associated with each medically attended RSV event
- Number and proportion of subjects with other common respiratory pathogens identified by a RT-PCR multiplex respiratory panel which is distinct from the RT-PCR assay being used to test for RSV for the study's efficacy endpoints.

Note: Only nose swab specimens determined to be negative for RSV using the RT-PCR assay being utilized for evaluation of the study's efficacy endpoints will be evaluated by the RT-PCR multiplex respiratory panel. RSV positive samples identified by the RT-PCR multiplex respiratory panel will not be taken into account for the purpose of the analysis of the study's efficacy endpoints.

a A pediatric clinic visit represents any outpatient medically attended visit that could include, but is not limited to, a pediatric clinic visit, a primary physician office visit, a family physician visit, or a study site visit.

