# 9.5.2.3. Exploratory Analysis

Pharmacoeconomic variables will be summarized descriptively for Part B.

Respiratory syncytial virus confirmed hospitalization, a component of the primary composite endpoint, will be explored using the same statistical methodology as the primary efficacy analysis. For this exploratory analysis, the 2 REGN2222 treatment groups will be combined for comparison to the placebo group, with the intent to evaluate the REGN2222 effect on subjects with RSV confirmed hospitalization.

Pharmacoeconomic variables and proportion of subjects with other common respiratory pathogens identified by a RT-PCR multiplex respiratory panel will be summarized descriptively for Part B. Only nose swab specimens determined to be negative for RSV using the RT-PCR assay being utilized for evaluation of the study's efficacy endpoints will be evaluated by the RT-PCR multiplex respiratory panel.

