During the 150-day efficacy assessment period, data will be collected on subjects with any acute respiratory illness requiring medical attention. After enrollment of their infant into the study, parent(s) or guardian(s) taking their enrolled infant to a healthcare provider (inpatient or outpatient, including hospitalizations, ER, UC, or pediatric clinic) will be asked to contact the study staff immediately or soon after seeking medical attention for any of the following symptoms: fever, cough, earache, nasal congestion, rhinorrhea, vomiting after coughing, wheezing, or difficulty breathing (labored, rapid, or shallow).

When the parent(s) or guardian(s) takes their child for medical attention for an acute respiratory infection, they will be instructed to take a Medical Information Packet with them for the treating clinician. All infants who have a medically attended visit for a respiratory illness will be asked to have an unscheduled study visit as soon as possible or within 72 hours of discharge from the medical facility. Study site personnel will evaluate the subject during an unscheduled visit, including a history of the acute illness and nose swab collections for viral detection will occur. All nose swabs will be tested using a reverse-transcriptase polymerase chain reaction (RT-PCR) assay for RSV, which will be conducted in a central laboratory. All RSV isolates will be tested for their subtypes, specifically subtype A or subtype B. If the unscheduled study visit following a medically attended respiratory infection occurs >72 hours but <14 days of discharge from the medical facility, all procedures (as appropriate), including nose swab collection, should occur despite being outside of the 72 hour window. Unscheduled study visits for medically attended respiratory illness will be required through Day 150 even if a child has had a prior RSV-confirmed or other respiratory illness. Unscheduled study visits for medically attended respiratory illness will not be required between the day after the Day 150 visit and Day 237 (end of study) visit for the purpose of nose swab collection.

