- 14) Repeat items 9) through 13) above with the single exception to count the number of all-cause respiratory illness-associated visits **after** the initial episode of RSV illness.
- 15) Total number of days with RSV-associated mechanical ventilation for subjects with RSV-confirmed hospitalizations.
- 16) Total number of days with RSV-associated supplemental oxygen for subjects with RSV-confirmed hospitalizations.

- 17) Total length of stay in hospital for subjects with RSV-confirmed hospitalizations.
- 18) Total number of missed days of work for parent(s) or guardian(s) associated with each medically attended RSV event.
- 19) Number and prevalence rate of other common respiratory pathogens identified by a RT-PCR multiplex respiratory panel for nose swab specimens determined to be negative for RSV (using the protocol specified Lyra RT-PCR assay [Quidel Molecular RSV/hMPV assay]).
- 20) Proportion of FAS subjects with the primary endpoint event, with the single exception of using an alternative definition for LRTI.

Instead of the LRTI definition in Section 4.6.1, the following definition of LRTI will be used for medically attended RSV infection (hospitalization or outpatient LRTI) as agreed in the Pediatric Investigational Plan (PIP) :

Infant with RSV-proven infection who presents with cough or difficulty breathing **and 2** of the following criteria:

- Lower chest wall indrawing
- Hypoxemia (peripheral capillary oxygen saturation <95% breathing room air)
- Wheezing or crackles
- Ventilatory failure (needing ventilator support in any form)
- New onset apnea
- Increased respiratory rate using WHO criteria for fast breathing for age ([Wingerter 2012](#)) as below:

| Age | Increased Respiratory Rate (breaths/min) |
|--------------------|------------------------------------------|
| < 60 days | ≥ 60 |
| 60 - 364 days | ≥ 50 |
| 365 days - 5 years | ≥ 40 |

Age in days = Onset date of the episode of RSV illness – birth date +1.

- 21) Proportion of FAS subjects with the primary endpoint event, with the single exception of the removal of RSV hospitalization non-LRTI.
- 22) Proportion of FAS subjects with the primary endpoint, with the single exception of accepting positive RSV detection results from the multiplex RT-PCR respiratory panel in deriving the primary endpoint event.

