5.7.5.3. Non-RSV Medically Attended Respiratory Illness

To evaluate the effect of REGN2222 on the non-RSV MARI, the proportion of subjects who had medically attended respiratory illness (hospitalization or outpatient LRTI) not confirmed to be related to RSV (either all negative RSV or missing RSV testing results within 14 days since AE onset) will be summarized for each treatment group. If a subject had both non-RSV MARI and RSV MARI (ie, the primary endpoint event), they will not be included in the numerator when calculating the proportion. For this particular analysis, only observed events will be included as events. Treatment difference in this proportion will be summarized using descriptive statistics.

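### SAP 5.12 analyses a narrower multiplex-pathogen endpoint than the protocol defines: it counts only infants with a non-RSV hospitalization or outpatient LRTI and drops those who also had an RSV primary endpoint event

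*SAP*

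**What the plan says.** **Endpoint.** Protocol 8.4 lists the "Number and proportion of subjects with other common respiratory pathogens identified by a RT-PCR multiplex respiratory panel", and its note restricts panel testing to swabs that are RSV-negative on the study assay. Protocol 9.5.2.3 plans that the "proportion of subjects with other common respiratory pathogens identified by a RT-PCR multiplex respiratory panel will be summarized descriptively for Part B". SAP 4.6.3, item 19, names a "prevalence rate of other common respiratory pathogens identified by a RT-PCR multiplex respiratory panel for nose swab specimens determined to be negative for RSV". None of the three mentions LRTI or hospitalization.

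**Who is swabbed and tested.** SAP 2.3 states: "All infants who have a medically attended visit for a respiratory illness will be asked to have an unscheduled study visit", and swabs are collected at that visit. The trigger symptoms in Protocol 6.2.3 include fever, earache, nasal congestion and rhinorrhea. Protocol 6.3.3.3 adds that "nose swab specimens negative for RSV using the RT-PCR assay utilized for determination of primary endpoint cases will be evaluated using a second" assay, the multiplex panel.

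**What is counted.** SAP 5.12 puts in the numerator subjects "with non-RSV medically attended respiratory illness (as defined in Section 5.7.5.3) who tested positive for any and each type of non-RSV pathogen" and uses all FAS subjects in the arm as denominator. SAP 5.7.5.3 defines the illness as "medically attended respiratory illness (hospitalization or outpatient LRTI) not confirmed to be related to RSV". It also says that a subject with both a non-RSV illness and an RSV primary endpoint event is not included in the numerator.

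**Declared departures.** SAP 1.2.3 reports none from the protocol's statistical section.

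**The concern.** The endpoint and the laboratory testing cover RSV-negative swabs from any medically attended respiratory illness. The planned table covers only the more severe part of those illnesses, and only in infants who had no RSV primary endpoint event. A programmer who follows SAP 5.12 will produce a different number from the one that Protocol 8.4 names.

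The cost is interpretive. SAP 4.12 says that the panel was introduced after a comment from the US regulator, to explore other causes of RSV-negative respiratory tract infection. That purpose is not confined to lower-tract disease. A narrower table standing in for the endpoint would answer the question only in part. A reader comparing the study report with the protocol would not be told that the population had changed.

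**Working it through.** No figure in the plan needs reproducing, so the check sets the definition beside the counting rule.

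**Step 1. Apply both rules to typical infants.** Every infant below is in the FAS and has at least one RSV-negative swab positive for another pathogen.

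| Infant's illnesses | Case under Protocol 8.4 | Case under SAP 5.12 |
|---|---|---|
| A. Outpatient illness without LRTI only | Yes | No: not hospitalization or outpatient LRTI |
| B. Outpatient non-RSV LRTI, no RSV event | Yes | Yes |
| C. Hospitalized for a non-RSV upper respiratory illness, no RSV event | Yes | Yes: hospitalization limb |
| D. Pathogen-positive outpatient cold, plus a separate non-RSV LRTI, no RSV event | Yes | Yes: 5.12 does not tie the positive swab to the qualifying illness |
| E. Non-RSV LRTI, plus an RSV primary endpoint event | Yes | No: removed by 5.7.5.3 |

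The two rules part at A and E.

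**Step 2. Look for another SAP analysis that recovers A and E.**
- Items 22 and 23 of SAP 4.6.3 use RSV detections from the panel, not other pathogens.
- SAP 5.7.4 specifies no analysis for item 19.
- SAP 5.11 reports subjects swabbed and subjects with an RSV-positive swab. It does not report panel results.

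Nothing recovers them.

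**Step 3. What can be said about size.**
- *Loss A.* The documents give no rate of RSV-negative outpatient illness without LRTI and no panel positivity rate. No figure can be derived.
- *Loss E.* Only a ceiling follows from the planning assumptions in Protocol 9.2: about 1200 infants in three equal arms, a 10% placebo event rate and a 60% reduction.
  - Per arm: 1200 / 3 = 400.
  - Placebo infants with an RSV primary endpoint event: 0.10 × 400 = 40.
  - Each REGN2222 arm: 0.10 × (1 − 0.60) = 0.04, and 0.04 × 400 = 16.

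  These are the expected numbers of infants whom the exclusion could touch. Only those who also have a pathogen-positive, RSV-negative swab are lost from the protocol-defined count, and the documents do not give that share. If it were similar across arms and the drug worked as assumed, the exclusion would lower the placebo proportion more than the active ones.

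**The case against.** **The restriction is a sensible focus.** It matches the severity level of the primary endpoint and the illness category in SAP 5.7.5.3. That is a fair reason to keep the table. It does not explain why the protocol's endpoint has no row of its own, or why SAP 1.2.3 declares no change.

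**The protocol's summary is still owed.** Protocol 9.5.2.3 plans an unrestricted descriptive summary and the SAP declares no departure, so 5.12 could be read as an additional, focused table. This reading is possible, and it means that one cannot say the detections are discarded by design. But the SAP gives no specification for the unrestricted summary, and 5.12 is the only place where these results are analysed.

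**The same rule applies in every arm.** This is true of the severity filter. The RSV-event exclusion is also the same rule in each arm, but it acts on an outcome that treatment is meant to change.

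Three stronger readings are tempting, and the documents do not support them.
- A reader might infer that upper respiratory detections are never counted. Infants C and D show otherwise.
- A reader might infer that the FAS denominator makes the percentage too low. Protocol 8.4 asks for a proportion of subjects, and the FAS fits that. Only the numerator is at issue.
- A reader might infer that item 19 commits the sponsor to a swab-level prevalence. Item 19 states no denominator, and its reference to RSV-negative specimens may only identify which swabs go to the panel.

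**Conclusion.** The mismatch is real and minor. As written, SAP 5.12 reports a narrower quantity than Protocol 8.4 and 9.5.2.3 and SAP item 19. It omits infants whose only pathogen-positive, RSV-negative illness was outpatient without LRTI, and infants who also had an RSV primary endpoint event. The second omission rests on reading the cross-reference to 5.7.5.3 as carrying that section's numerator rule with it. This is the natural reading, but 5.12 does not restate the rule.

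The direction is an undercount relative to the protocol's definition. Its size is unknown: any percentage would only restate an assumed share of upper respiratory illness. The planning-rate ceilings of 40 and 16 infants per arm apply to the RSV-event exclusion alone.

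A reader might also infer a threat to the efficacy conclusions. There is none. Protocol 6.3.3.3 and SAP 4.12 keep panel results out of the primary and secondary endpoints, and this endpoint is exploratory and descriptive. Alpha and power are untouched.

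**What to change.** In SAP 5.12, summarize by arm the number and proportion of all FAS subjects with at least one RSV-negative swab positive for a non-RSV pathogen, for any pathogen and for each type. Apply neither the 5.7.5.3 filter nor its exclusion of subjects with an RSV primary endpoint event.

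Keep the present hospitalization/outpatient-LRTI table as a labelled subset row, and state there whether subjects with an RSV event are in or out. If the sponsor prefers the narrower table alone, SAP 1.2.3 should declare it as a departure from the protocol.

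Optionally, state the denominator for the prevalence rate in item 19, for example the number of RSV-negative swabs tested.

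The cost is SAP wording and an extra set of table rows. No new specimens, testing or data collection are needed.

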6. DATA CONVENTIONS

The following analysis conventions will be used in the statistical analysis.

6.1. Definition of Baseline for Efficacy/Safety Variables

Unless otherwise specified, the baseline assessment for all measurements will be the last chronologically available valid measurement taken prior to the administration of the first dose of study drug. For most variables, Day 1 procedures and assessments are considered to be baseline. For variables such as ADA, samples collected at the screening visit will be considered to be baseline.

